8.5.3 Physical examination

A physical examination must include:

- General appearance
- Head, ears, eyes, nose, throat, neck
- Respiratory system
- Cardiovascular system
- Gastrointestinal system including mouth
- Musculoskeletal system
- Central and peripheral nervous system
- Skin
- Abdomen
- Lymph node palpation
- Thyroid gland

8.5.4 Vital Signs

Diastolic blood pressure, systolic blood pressure and pulse rate should be measured while the subject is in a sitting position and after 5 minutes of rest.

At V1 the blood pressure must be measured three times and all three values must be entered in the eCRF. The mean value will be calculated by the system and must be in accordance with the relevant exclusion criteria (see section 6.3). At the following visits, the blood pressure should only be measured once.

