6.3 Exclusion criteria

For an eligible subject, all exclusion criteria must be answered "no".

- 1. Known or suspected hypersensitivity to trial product(s) or related products.
- 2. Previous participation in this trial. Participation is defined as signed informed consent.
- 3. Receipt of any investigational medicinal product within 90 days prior to screening.
- 4. Female who is pregnant, breast-feeding or intends to become pregnant or is of child-bearing potential and not using adequate contraceptive methods (adequate contraceptive measures as required by local regulation or practice).
- 5. Use of any OADs (other than SGLT2i in monotherapy or in combination with metformin or DPP4i or pioglitazone as described in the inclusion criteria) within 90 days prior to the day of screening.
- 6. Use of GLP-1 receptor agonist (e.g., exenatide or liraglutide) within 90 days prior to the day of screening.
- 7. Acute decompensation of glycaemic control requiring immediate intensification of treatment to prevent severe metabolic dysregulation (e.g., diabetes ketoacidosis) in the previous 90 days prior to the day of the screening.
- 8. Family or personal history of multiple endocrine neoplasia type 2 or medullary thyroids carcinoma.
- 9. Screening calcitonin \geq 50 ng/L.
- 10. History of pancreatitis (acute or chronic).
- 11. Any of the following: myocardial infarction, stroke or hospitalisation for unstable angina and/or transient ischaemic attack within the past 180 days prior to the day of screening.
- 12. Subjects presently classified as being in NYHA Class III or IV.
- 13. Planned coronary, carotid or peripheral artery revascularisation at the day of screening.
- 14. Renal impairment eGFR < 60 mL/min/1.73 m² as per CKD-EPI.
- 15. Impaired liver function, defined as ALT \geq 2.5 times upper normal limit at screening.
- 16. Inadequately treated blood pressure as defined as Class 2 hypertension or higher (systolic ≥ 160 mmHg or diastolic > 100 mmHg) at screening.
- 17. Anticipated initiation or change in concomitant medications for more than 14 consecutive days or on a frequent basis known to affect weight or glucose metabolism (e.g., orlistat, thyroid hormones, corticosteroids).

- 18. Proliferative retinopathy or maculopathy requiring acute treatment. Verified by fundus photography or dilated fundoscopy performed within 90 days prior to randomisation.

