8.1.2 Screening (V1)

Screening visit and all screening assessments must take place within 14 calendar days prior to randomisation (V2).

Informed consent process

Prior to screening, the investigator must provide the subject with verbal and written information about the trial. Informed consent must be obtained before any trial related activity, see section 18.2. The date of informed consent must be transcribed to the eCRF for all screened subjects.

Screening

Screening of subjects will be registered by using IWRS (see section 10). Each subject will be assigned a unique 6-digit subject number which will remain the same throughout the trial. The first three digits in the subject ID number will consist of the site number and the last three digits of the subject ID number will indicate the individual subject number.

All inclusion and exclusion criteria must be reviewed and if any criteria cannot be assessed e.g. criteria related to results from blood sampling performed at screening or if a valid eye examination is missing, the investigator must ensure these are obtained for assessment of eligibility prior to the randomisation of the subject.

At screening, subjects will be provided with a card stating that they are participating in a trial and giving contact address(es) and telephone number(s) of relevant trial site staff. Subjects should be instructed to return the card to the investigator at the last trial visit, or instructed to destroy the card after the last phone contact.

The investigator must keep a subject screening log, a subject identification code list and a subject enrolment log. The subject screening log and subject enrolment log may be combined in one list.

8.1.3 **Screening failures**

If a screened subject for any reason is not eligible or are not randomised within 14 calendar days after the screening visit (V1), the subject will be considered a screening failure. For screening failures the screening failure form in the eCRF must be completed with the reason for not continuing in the trial. Serious and non-serious AEs from screening failures must be transcribed by the investigator into the eCRF. Follow-up of SAEs must be carried out according to section 12.3. Screening failures experiencing an AE that would otherwise qualify for adjudication (see section 12.7) will not be adjudicated as no trial product has been administered.

A screening failure session must be made in the IWRS. The case book must be signed.

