Date: Version: Status: Page:

20 November 2015 | Novo Nordisk 2.0 Final 70 of 107

treating individual subjects with T2DM. For the confirmatory secondary endpoints de jure estimands addressing efficacy are chosen as secondary estimand too.

Only endpoints derived after 26 weeks will be analysed statistically. The expected percentage of missing data is around 15%. In accordance with guidance $\frac{29}{2}$ endpoints will be assessed at frequent visits and also on subjects who prematurely discontinue treatment. If an assessment has been made both at screening and randomisation, and if not otherwise specified, the value from the randomisation visit will be used as the baseline value. If the value measured at the randomisation visit is missing and the assessment also has been made at screening, then the screening value will be used as the baseline value.

Laboratory values below the lower limit of quantification (LLOQ) will be set to ½LLOQ.

The test strategy is hierarchical testing in order to control the familywise Type I error. Inferences will be based on the primary analyses of the primary estimands. The trial will be powered with respect to the primary objective and endpoint.

Presentation of results from a statistical analysis will include the estimated mean treatment effects using LSMean for absolute values, and change from baseline where applicable. The LSMean is either obtained by Rubin's rule weighing together LSMeans from multiple imputation estimations or obtained directly from estimation of a parameterized statistical model. In addition, estimated mean treatment difference (or ratio) will be presented together with the two-sided 95% confidence interval and corresponding two-sided *p*-value.

In the statistical models explanatory factors will be parameterized as follows:

- Treatment: IDegLira, IGlar
- Pre-trial OAD: SGLT2i ± pioglitazone(pio), SGLT2i + metformin(met) ± pio, SGLT2i + $DPP4i \pm pio$, $SGLT2i + met + DPP4i \pm pio$
- Region: Europe (Finland, Hungary, Russia, Slovakia, Slovenia, Spain, Switzerland), North America (CA, USA), South America (Argentina), Asia (India)
- Visit: Planned visits for actual endpoint according flow-chart

The impact of protocol deviations and outliers may be investigated further in sensitivity analyses if deemed relevant.

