- In the fourth step, for each of the 1000 copies of the dataset, missing HbA_{1c} values at the second planned HbA_{1c} measurement visit after randomisation (V14) are imputed in the same way as in the previous step, now based on an ANOVA model with pre-trial OAD and region as factors, and the HbA_{1c} values at baseline and at previous planned HbA_{1c} measurement visits as covariates, fitted to the control group (IGlar) and subjects with retrieved (V32A) data in the investigational group (IDegLira)
- This fourth step is then repeated sequentially over visits where HbA_{1c} measurement is planned, adding one visit in each step until the last planned visit (V32)
- In the sixth step a penalty equal to the non-inferiority margin 0.3% is added to the EOT HbA_{1c} value for any prematurely discontinued subject in the investigational group (IDegLira), irrespective of the EOT value being retrieved (V32A) data or an imputed value from the sequential imputation steps (step 3 to 5)

• In the seventh step, for each of the 1000 complete data sets, the change from baseline to the EOT visit (V32) is analysed using an ANOVA model with treatment, pre-trial OAD and region as factors and baseline HbA_{1c} value as a covariate

• In the eighth step, the estimates and standard errors for the 1000 data sets are pooled to one estimate and associated standard error using Rubin's rule³⁷. From these pooled estimates the confidence interval for the treatment difference and the associated *p*-value are calculated

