Change from baseline in mean of the 9-point profile and prandial increment endpoints will be analysed separately by multiple imputation J2R.

Blood pressure (systolic and diastolic) change from baseline after 26 weeks

Change from baseline in systolic and diastolic blood pressure will be analysed separately by multiple imputation J2R.

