2.24 Section 17.4.2.1 Efficacy endpoints

For each of the multiple copies (1000) of the full dataset of the primary analysis of the primary estimand (unconditional multiple imputation J2R with retrieved data, NI penalty section 2.19) the responder endpoints are derived without using the non-inferiority penalty (step 6) and analysed with the standard logistic regression model. Estimates are pooled using Rubin's rule³/.

Waist circumference change from baseline after 26 weeks

Change from baseline in waist circumference will be analysed by unconditional multiple imputation J2R.

Fasting plasma glucose change from baseline after 26 weeks

Change from baseline in FPG will be analysed by *unconditional* multiple imputation J2R.

Fasting lipid profile after 26 weeks

Cholesterol, LDL cholesterol, HDL cholesterol, VLDL cholesterol, triglycerides and free fatty acids will be analysed separately by *unconditional* multiple imputation—J2R. In these statistical analyses, the endpoint will be log-transformed and so will the corresponding baseline covariate.

Self-measured plasma glucose (SMPG) 9-point profile change from baseline after 26 weeks

A linear mixed effect model will be fitted to the 9-point SMPG profile data. The model will include treatment, pre-trial OAD, time (within 9-point profile), the interaction between treatment and time, the interaction between pre-trial OAD and time as fixed factors, and subject as random effect, where measurements within subjects will be assumed correlated as specified by a compound symmetric covariance matrix. From the model mean profile by treatment and relevant treatment differences will be estimated and explored.

Change from baseline in mean of the 9-point profile and prandial increment endpoints will be analysed separately by *unconditional* multiple imputation-J2R.

Blood pressure (systolic and diastolic) change from baseline after 26 weeks

Change from baseline in systolic and diastolic blood pressure will be analysed separately by unconditional multiple imputation J2R.

Protocol Amendment 2 Trial ID: NN9068-4229 UTN:U1111-1168-9343

EudraCT No.: 2015-001596-48

CONFIDENTIAL

Date: Version: Status: Page:

28 November 2016 | Novo Nordisk Final 18 of 19

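### The systolic and diastolic models adjust only for the single V2 reading; adding the V1 three-reading mean as a second baseline covariate would modestly narrow their intervals at almost no cost

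*Protocol*

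**What the plan says.** - **Measurement.** Protocol section 8.5.4 requires three blood pressure readings at V1; "all three values must be entered in the eCRF" and the system calculates their mean. For later visits it says "At the following visits, the blood pressure should only be measured once". The flow chart schedules vital signs at V1, V2, V18 and V32.
- **Use of the V1 mean.** It is checked against exclusion criterion 16 in section 6.3 ("Inadequately treated blood pressure as defined as Class 2 hypertension or higher").
- **Baseline rule.** Section 17 covers assessments made at both screening and randomisation: unless otherwise specified, "the value from the randomisation visit will be used as the baseline value". The screening value serves only when the V2 value is missing. The protocol specifies nothing else for blood pressure.
- **Analysis.** Section 17.4.2.1 states: "Change from baseline in systolic and diastolic blood pressure will be analysed separately by multiple imputation J2R". Amendment 2 relabels this method as unconditional multiple imputation and leaves the covariates alone. The method is the HbA1c one in section 17.3.1. Its imputation steps use pre-trial OAD, region, the baseline value and earlier visits. Its final step is an "ANOVA model with treatment, pre-trial OAD and region as factors and baseline HbA_{1c} value as a covariate", with blood pressure taking the place of HbA1c here.

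**The concern.** A single reading carries both visit-to-visit and reading-to-reading noise. A covariate measured with noise explains less of the week-26 variance than two pre-randomisation visits taken together. The trial already holds the second visit's value in the database for every eligible subject, because eligibility depends on it. Leaving it out of the models makes the confidence intervals for the systolic and diastolic treatment differences wider than they need to be. Only the precision of two supportive endpoints is at stake. Bias, the estimand and error control are not affected.

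**Working it through.** **The plan's own figures.** The protocol states no standard deviation, power or precision for blood pressure. Its one sample size calculation is for HbA1c and it reproduces: 176 evaluable per arm / 0.85 = 207.1, rounded up to 208. It has no bearing on blood pressure precision. Every variance and correlation below is therefore an assumption.

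**Formula.** The width of the interval is proportional to the square root of the residual variance of the V32 value given the baseline covariates. Scale a single reading to variance 1 and let

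- rY = correlation of a pre-randomisation reading with V32,
- r12 = correlation of V1 with V2,
- w = share of variance between readings within a visit, so the V1 mean of three has variance v = 1 − 2w/3.

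Residual variance with V2 only: 1 − rY².
Residual variance with V2 and the V1 mean: 1 − rY²(1 + v − 2·r12)/(v − r12²).

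**Worked case** (rY = 0.5, r12 = 0.6, w = 0.1, so v = 0.9333).
V2 only: 1 − 0.25 = 0.75.
Both: 1 − 0.25 × 0.7333/0.5733 = 0.680.
Width ratio √(0.680/0.75) = 0.952, or 4.8% narrower.

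**Range over assumed correlations** (w = 0.05 to 0.20, no truncation, no imputation):

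| rY | r12 | Narrowing |
|---|---|---|
| 0.4 | 0.4–0.6 | 2.5–5% |
| 0.5 | 0.5–0.7 | 3–7% |
| 0.6 | 0.6–0.8 | 3.5–9% |
| 0.7 | 0.7–0.8 | 6–12% |

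The 12% needs a correlation of 0.7 that is no lower over 26 weeks than over the screening interval, together with the largest w. It ignores eligibility truncation and imputation, so I do not rely on it.

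**Check with variance components** (systolic, in mmHg²: stable between-subject 100–140, visit 50–80, reading 20–30). With a 26-week correlation of the stable part of 0.85–1.0 and independent visit noise, the width ratio is 0.905–0.960.

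- *Favourable corner* (140, 50, 20; correlation 1.0). V2 only: 210 − 140²/210 = 116.7. Both: 210 − 140² × (210 + 196.67 − 280)/(210 × 196.67 − 140²) = 95.6. Ratio √(95.6/116.7) = 0.905.
- *Correlated visit noise.* V1 and V2 are about two weeks apart at most by the flow chart, so their visit noise may be correlated. At 0.2, 0.4 and 0.6 the ratio becomes 0.919–0.967, 0.931–0.974 and 0.942–0.980.
- *Unfavourable corner* (100, 80, 20; 26-week correlation 0.60; visit-noise correlation 0.6, so the V1–V2 covariance is 100 + 48 = 148). V2 only: 200 − 60²/200 = 182.0. Both: 200 − 60² × (200 + 186.67 − 296)/(200 × 186.67 − 148²) = 178.8. Ratio √(178.8/182.0) = 0.991, about 1%.

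**Design-like simulation.** 416 subjects, V1 mean truncated at 160 mmHg, 15% discontinuing, reference-based imputation through V18 and V32, Rubin's rule, w = 0.1. Over six correlation settings the standard error ratio ran from 0.930 (rY = r12 = 0.6) to 0.976 (rY = 0.4, r12 = 0.6), that is 2–7% narrower. The treatment estimates with and without the extra covariate differed by at most 0.05 mmHg.

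**Where the gain comes from.** In the worked case, one V1 reading in place of the mean (v = 1) leaves 1 − 0.25 × 0.8/0.64 = 0.6875. The ratio is √(0.6875/0.75) = 0.957, against 0.952 with the mean. Over the variance-component grid with independent visit noise, the average ratio is 0.945 for a single V1 reading and 0.937 for the mean of three. The triplicate adds under one percentage point.

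**Cost of the extra parameter.** With 416 subjects and 9 parameters in the current model (intercept, treatment, 3 for OAD, 3 for region, 1 baseline), one more gives √(407/406) = 1.0012, about 0.1% of width.

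**The case against.** The strongest reply is that nothing here is an error. The measurement rule, baseline rule and model are mutually consistent. One randomisation-visit baseline applied uniformly across endpoints is conventional and valid, and the protocol promises no precision for blood pressure. That stands, and it is why the point is only an improvement.

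It also stands that the same reasoning would apply to other variables measured at both V1 and V2, such as HbA1c, body weight and pulse. This is a covariate choice more than a flaw peculiar to section 8.5.4. The baseline rule does leave room for a different specification, and the SAP is not at hand. However, the protocol itself fixes the rule and the model, and it names endpoint-specific covariates where it wants them: baseline HbA1c for insulin dose (section 17.4.1.1) and baseline weight in the composite responder models (section 17.4.2.1). A second baseline covariate for one endpoint would fit that practice.

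A reader might infer more than the documents support:

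- *That the V1 value is thrown away.* It is not. It decides eligibility and is the fallback baseline.
- *That the triplicate reading is what is being lost.* Nearly all the gain comes from the second visit.
- *That the V2-only analysis is biased, or that V1 should replace V2 as baseline.* Neither follows. V2 is a valid baseline, and the gain comes from using both.
- *That the change is entirely free.* It takes one parameter and a departure from the common model, and truncation by the exclusion limit trims the information in V1.

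**Conclusion.** The point holds as a small efficiency gain. When V2 is present, the systolic and diastolic models adjust for one V2 reading and leave a second pre-randomisation value unused as a covariate. Because V1 precedes randomisation, adding it does not bias the treatment contrast.

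The size cannot be fixed from the documents. Under the assumed correlations and variance components, a fair figure is 2–7% narrower intervals. By 1/0.98² = 1.04 and 1/0.93² = 1.16, that is worth about 4–16% more subjects for these endpoints. It falls to about 1% if visit noise at V1 and V2 is strongly correlated and the 26-week correlation is low, and reaches about 9% on the most favourable variance components. Blood pressure is supportive and outside the hierarchy in section 17.4.1, so no confirmatory conclusion, estimand or error rate changes.

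**What to change.** For systolic and diastolic pressure only, keep V2 as the baseline from which the change is calculated. Add the V1 three-reading mean as a second baseline covariate in the sequential imputation ANOVAs (steps 3–5 of section 17.3.1) and in the final ANOVA (step 7). State this before data are released for analysis, and state how a subject with V2 missing is handled, since the V1 mean would then already be the baseline. The cost is one sentence, one degree of freedom and a model line specific to these two endpoints. No new data or visit is needed.

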8.5.5 Electrocardiogram (ECG)

A 12-lead ECG must be performed by the investigator or delegated staff. The ECG must be interpreted, signed and dated by the investigator to verify that the data has been reviewed. The ECG at screening must be done at the latest at V2 and the results interpreted by the investigator prior to determine the eligibility of the subject.

The evaluation transcribed to the eCRF must follow the categories:

- Normal
- Abnormal
 - Was the result clinically significant? (Yes/No)

8.5.6 Eye examination

An eye examination (dilated fundoscopy/fundus photography) must be performed by the investigator, a local ophthalmologist or an optometrist according to local practise. Results of the eye examination must be interpreted, signed and dated by the investigator to verify that the data has been reviewed before randomisation and in order to determine the eligibility of the subject.

The evaluation of the results must follow the categories:

- Normal
- Abnormal
 - Was the result clinically significant? (Yes/No)

If an eye examination has been performed within 12 weeks prior to V2 the procedure does not need to be repeated, if the results are available for evaluation at V2. If the eye examination is performed before the subject consented to participate in the trial, it must be stated in the subject's medical records that the procedure was not performed in relation to this trial.

If an eye examination has been performed within 2 weeks prior to V32 the procedure does not need to be repeated, if the results are available for evaluation at V32.

8.5.7 Blood samples for safety

Blood samples will be drawn in accordance with the flow chart (section $\underline{2}$) and analysed by the central laboratory to determine levels of the following laboratory parameters:

Haematology: Erythrocytes, haematocrit, haemoglobin, leucocytes, thrombocytes, differential count (eosinophils, neutrophils, basophils, monocytes and lymphocytes).

Biochemistry: Amylase, lipase, ALT, AST, alkaline phosphatase, albumin, bilirubin (total), creatinine, potassium, sodium, calcium (ionized), urea, GFR (estimated).

Hormones: Blood samples for the measurement of calcitonin concentration will be drawn as per flow chart (see section $\underline{2}$). In case any calcitonin value at any time of the trial is ≥ 10 ng/L the algorithm in appendix C Monitoring of calcitonin must be followed.

Pregnancy test: Females of childbearing potential will have a human chorionic gonadotropin (hCG) serum pregnancy test performed according to the flow chart (section $\underline{2}$).

Protocol
Trial ID: NN9068-4229
UTN: U1111-1168-9343

Date: 20 November 2015 | Novo Nordisk
Version: 2.0
Status: Final

Page:

45 of 107

8.5.8 Urine test for safety

EudraCT No.: 2015-001596-48

A urine sample must be collected at V1, V18 and V32 to determine the **albumin/creatinine ratio**, see flow chart (section 2). The analysis will be performed by the central laboratory.

Urine dipstick test must be performed at the site according to the flow chart, section 2. The following parameters will be tested; glucose, ketone, nitrite, pH, protein, leucocyte, and erythrocyte.

Urine pregnancy test using urine dipsticks will be performed at site during the trial for females of childbearing potential if a menstrual period is missed or pregnancy is suspected. If a urine test is positive, a confirmatory serum-hCG test must be taken and sent to the central laboratory for analysis. It should be documented in the eCRF in an unscheduled visit, describing "pregnancy test" under "other".

